6.3 Assignment to Treatment Groups

The Investigator or delegate will assign a unique subject identifier number to eligible subjects in chronological order at the time of informed consent signature. Subject identifiers will be comprised of digits representing the trial number, the site number, and the subject number, which is allocated sequentially. Subject enrollment will be managed manually during the escalation phase and for the NSCLC biomarker cohort. Enrollment for other expansion cohorts will utilize an interactive web response system (IWRS).

NSCLC second-line cohort

Once the subject has provided a signed Informed Consent Form (ICF) and meets all inclusion and no exclusion criteria, the Investigator or delegate will request the dose group assignment using the IWRS. Qualified subjects will be randomized in a 1:1 ratio to receive either 500 or 1200 mg/infusion of MSB0011359C. The cohort is fully controlled by the IWRS, which assigns treatment individual (unique) vial numbers for each subject. The vial number is linked via the Good Manufacturing Practice qualified system to the corresponding treatment as well as to the subject. Allocation of subjects will not be stratified.

6.4 Noninvestigational Medicinal Products to be Used

In order to mitigate potential infusion-related reactions, premedication with an antihistamine and with paracetamol (acetaminophen) (for example, 25-50 mg diphenhydramine and 500-650 mg paracetamol [acetaminophen] IV or oral equivalent) approximately 30 to 60 minutes prior to each dose of MSB0011359C is mandatory for the first 2 infusions and is optional and at the discretion of the Investigator after the second infusion (premedication is optional for all infusions for subjects in the NSCLC biomarker cohort being treated at the US NCI). If Grade ≥ 2 infusion reactions are seen during the first two infusions premedication should not be stopped. This regimen may be modified based on local treatment standards and guidelines as appropriate. Steroids as premedication are not permitted.

As with all monoclonal antibody therapies, there is a risk of allergic reaction including anaphylactic shock. MSB0011359C should be administered in a setting that allows for immediate access to an intensive care unit or equivalent environment and administration of therapy for anaphylaxis, such as the ability to implement immediate resuscitation measures. Steroids (dexamethasone 10 mg), epinephrine (1:1,000 dilution), allergy medications (IV antihistamines), bronchodilators, or equivalents, and oxygen should be available for immediate access. Infusion of MSB0011359C will be stopped in case of Grade ≥ 2 infusion-related, allergic, or anaphylactic reactions. Following MSB0011359C infusions, subjects must be observed for a minimum of 2 hours post end of infusion for potential infusion-related reactions, except note that during the first 2 doses in the escalation phase there will be a minimum 24-hour inpatient observation. Please see the guidelines for handling of infusion-related reaction in Section 6.5.4.1.

If an allergic reaction occurs, the subject must be treated according to the best available medical practice. Guidelines for management of infusion-related reactions and severe hypersensitivity reaction according to the NCI are found in Section 6.5.4.

Further precautions are provided in Section 6.5.4. For prophylaxis of flu-like symptoms, a non-steroidal anti-inflammatory drug (NSAID) for example, ibuprofen 400 mg or comparable NSAID dose, may be administered 2 hours before and 8 hours after the start of each dose of MSB0011359C IV infusion.

6.5 Concomitant Medications and Therapies

All concomitant medications taken by the subject during the trial, from the date of signature of informed consent are to be recorded in the appropriate section of the eCRF, noting the name, dose, duration and indication of each drug. Nondrug interventions (other than vitamins) and any changes to a concomitant medication or other intervention should also be recorded in the eCRF.

6.5.1 Permitted Medicines

Any medications (other than those excluded by the clinical trial protocol) that are considered necessary to protect subject welfare and will not interfere with the trial medication may be given at the Investigator's discretion.

Other drugs to be used for prophylaxis, treatment of anaphylactic reactions, infusion-related reactions, and severe hypersensitivity reactions / flu-like symptoms and irAEs are described in Sections 5.1.7.2, 6.4, and 6.5.4.

Palliative radiotherapy delivered in a normal organ-sparing technique may be administered during the trial. The assessment of PD will not be based on the necessity for palliative radiotherapy.

6.5.2 Prohibited Medicines

As stated for the exclusion criteria in Section 5.3.2, subjects must not have had chemotherapy, radiotherapy (other than palliative radiotherapy delivered in a normal organ-sparing technique as described in Section 6.5.1), major surgery, or received another investigational agent within 28 days before the start of trial treatment.

The following treatments must not be administered during the trial:

- Immunotherapy including interferon, immunosuppressive drugs (for example, chemotherapy or systemic corticosteroids except for short term treatment of allergic reactions, endocrine replacement therapy at low-dose prednisone [≤ 10 mg daily] or equivalent, or for the treatment of irAEs or other appropriate short-term steroid use), or other experimental pharmaceutical products. Short term administration of systemic steroid or other immunosuppressant such as infliximab or mycophenolate (that is, for allergic reactions or the management of irAEs) is allowed. Steroids with no or minimal systemic effect (topical, inhalation) are allowed. **Note:** for subjects with glioblastoma, steroid use is allowed.
- Adefovir.
- Prophylactic use of corticosteroids for infusion-related reactions is prohibited.
- Any live vaccine therapies for the prevention of infectious disease. Administration of inactivated vaccines is allowed (for example, inactivated influenza vaccines).
- Blood transfusions and erythroid growth factors are not allowed during the 21-day DLT window during the escalation phase.

If the administration of a non-permitted concomitant drug becomes necessary during the trial, the subject will be withdrawn from trial treatment (the Medical Monitor may be contacted to discuss whether the IMP must be discontinued).

Medications other than those specifically excluded in this trial (as outlined in this section) may be administered for the management of symptoms associated with the administration of MSB0011359C as required. These might include analgesics, anti-emetics, antihistamines, diuretics, anti-anxiety medications, and medication for pain management, including narcotic agents.

Any additional concomitant therapy that becomes necessary during the trial and any change to concomitant drugs must be recorded in the corresponding section of the eCRF, noting the name, dose, duration, and indication of each drug.

6.5.3 Other Interventions

The following non-drug therapies must not be administered during the trial (and within 28 days before the start of trial treatment):

- Major surgery (excluding prior diagnostic biopsy)
- Herbal remedies with immunostimulating properties (for example, mistletoe extract) or known to potentially interfere with major organ function (for example, hypericin)
- Subjects should not abuse alcohol or other drugs during the trial.

6.5.4 Special Precautions

For subjects enrolled in this study prior to the declaration of the MTD or the dose to be used in the expansion phase of the study (in the case MTD is not reached), in-house observation in a hospitalized setting for at least 24 hours will occur for the first 2 doses administered to each subject (Table 5). To facilitate PK and biomarker sampling, subjects may remain in-house through an additional 24 hours if necessary. A nurse, nurse practitioner / physician's assistant, or physician will communicate with the first subject of each cohort after the first treatment to assess for any side effects on or after Day 5 but before enrolling a subsequent subject. Cohorts at a dose that has been cleared by the SMC will require a minimum of 48 hours between the first dose administration in the first subject and first dose in subsequent subjects.

Once the MTD / dose to be used in the expansion phase of the study has been declared there is no waiting period between dosing of subjects.

Table 5 Wait Periods Between Dosing of Subjects Within a Dose / Expansion Cohort

	Before MTD/Phase II Dose Declaration / Before Dose Clearance	Before MTD/Phase II Dose Declaration / After Dose Clearance ^a	After MTD/Phase II Dose Declaration
In-house (hospitalization) observation	24 hours	None	None
Wait period between first subject first dose and subsequent subjects in a cohort	5 days	48 hours	None

HCC = hepatocellular carcinoma; MTD = maximum-tolerated dose; SMC = Safety Monitoring Committee.

^a Subjects in the HCC ascending-dose cohort may begin enrolling prior to declaration of the MTD / dose to be used in the expansion phase of the study by the SMC; however, the SMC must have cleared the starting dose for the HCC cohort as safe in the dose-escalation phase of the study.

As a routine precaution, subjects all enrolled in this trial (that is, both the dose-escalation and the expansion cohorts) must be observed for 2 hours post end of infusion, in an area with resuscitation equipment and emergency agents. At all times during MSB0011359C treatment, immediate emergency treatment of an infusion-related reaction or a severe hypersensitivity reaction according to institutional standards must be assured. In order to treat possible anaphylactic reactions, for instance, dexamethasone 10 mg and epinephrine in a 1:1000 dilution or equivalents should always be available along with equipment for assisted ventilation.

Infusion of MSB0011359C will be stopped in case of Grade ≥ 2 hypersensitivity, inflammatory response, or anaphylactic reaction. The treatment recommendations for infusion-related reactions and severe hypersensitivity reactions according to the NCI are outlined in Sections 6.5.4.1 and 6.5.4.2, respectively.

Investigators should also monitor subjects closely for potential irAEs, which may become manifest after several weeks of treatment. Such events may consist of persistent rash, diarrhea and colitis, autoimmune hepatitis, arthritis, glomerulonephritis, cardiomyopathy, or uveitis and other inflammatory eye conditions.

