and with paracetamol (acetaminophen) (for example, 25-50 mg diphenhydramine and 500-650 mg paracetamol [acetaminophen] IV or oral equivalent) approximately 30 to 60 minutes prior to each dose of MSB0011359C is mandatory for the first 2 infusions, after which premedication is optional and at the discretion of the Investigator. Steroids as premedication are not permitted.

As the 20 mg/kg cohort in the dose escalation portion has cleared SMC evaluation, an additional cohort at the 30 mg/kg dose level will be initiated, in parallel to the ongoing expansion cohorts. The 30 mg/kg cohort will be enrolled in a 3 + 3 design with SMC evaluation after the first 3 subjects and no more than 6 evaluable subjects to be enrolled. This cohort should provide additional insight into dose proportionality of PK and CCI parameters and support safety considerations at higher exposures than the expansion-phase dose of 1200 mg once every 2-weeks.

With the safety of the 30 mg/kg cohort established, a fixed dose cohort of 2400 mg once every 2 weeks will be enrolled in a 3 + 3 design with SMC evaluation after the first 3 subjects and no more than 6 evaluable subjects to be enrolled. This cohort should support safety considerations at higher exposures than the current expansion phase dose of 1200 mg once every 2 weeks, including those for alternative dosing regimens in Phase II and Phase III studies.

For PK / CCI purposes, after at least the first 2 cohorts have been evaluated with acceptable safety and for exploratory PK / CCI relationships, a decision will be made to initiate up to 2 cohorts of 3 subjects each, one at 0.1 mg/kg and one at 0.3 mg/kg, which will increase on the second dose and all subsequent doses to a 1200 mg/infusion flat dose dependent upon SMC clearance and only if the Sponsor and Coordinating Investigator have determined a meaningful dose for the intrasubject escalation. After the MTD has been reached or the 20 mg/kg cohort has been declared by the SMC as the highest non-MTD dose assessed, then further PK analyses may be performed. If deemed necessary, the 1, 3, 10, and 20 mg/kg cohorts may each enroll up to an additional 10 subjects (up to 40 total) for the purpose of establishing the PK / CCI relationship. On the second dose and all subsequent doses, the 1 mg/kg cohort may increase to a 1200 mg/infusion flat dose. No DLT evaluations will be performed in these supplemental cohorts.

Expansion

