After the MTD has been reached or the 20 mg/kg cohort has been declared by the SMC as the highest non-MTD dose assessed, then further PK analyses may be performed. If deemed necessary, the 1, 3, 10, and 20 mg/kg cohorts may each enroll up to an additional 10 subjects (up to 40 total) for the purpose of PK profile and possible PK / CCI modeling if there has been SMC clearance at the higher or same (20 mg/kg) dose level. On the second dose and all subsequent doses, the 1 mg/kg cohort may increase to a 1200 mg/infusion flat dose. No DLT evaluations will be performed in these supplemental cohorts. These lower dose cohort expansions for PK profile and PK / CCI purposes may proceed in parallel with the expansion cohorts if deemed appropriate by the Sponsor and Coordinating Investigator based on the MTD alone.

In the cohorts receiving 0.1 mg/kg and 0.3 mg/kg and in the additional subjects enrolled for the purpose of PK profile and possible PK / CCI modeling, it is intended to intensify the PK analysis by taking 3 additional PK samples during the first treatment cycle. These samples are scheduled to be taken at 8 to 12 hours, 3 to 5 days, and 10 to 12 days after the initiation of the first infusion of the study drug. The samples are to be taken at any time during these intervals. Exact sampling time must be recorded. These samples are labelled as optional in the Schedule of Assessments (Table 3) but they are highly important to allow a sufficiently detailed analysis and description of the MSB0011359C PK profile.

As the 20 mg/kg cohort in the dose escalation portion has cleared SMC evaluation, additional cohorts at 30 mg/kg and 2400 mg flat dose will be initiated, in parallel to the ongoing expansion cohorts. The 30 mg/kg and the 2400 mg flat-dose cohorts will be enrolled in a 3 + 3 design with SMC evaluation after the first 3 subjects and no more than 6 evaluable subjects to be enrolled. These cohorts should provide additional insight into dose proportionality of PK and CCI parameters and support safety considerations at higher exposures than the current expansion phase dose of 1200 mg once every 2 weeks.

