5.1.1.2 Expansion Cohorts

The dose for the expansion cohorts was determined by the Sponsor based on the safety observations and PK / CCI data from the dose escalation part of the trial. The flat doses for extension part will be implemented after clearance of 20 mg/kg escalation cohort by the SMC. Except for the second-line NSCLC cohort, all subjects in expansion cohorts will be receiving 1200 mg (flat dose) every 2 weeks. Subjects in the second-line NSCLC cohort will be randomized to receive either 500 or 1200 mg every 2 weeks (see Section 3.4.1.1 for rationales).

Subjects in the expansion cohorts will receive MSB0011359C as a 1-hour IV infusion once every 2 weeks until PD has been confirmed by a subsequent scan, unacceptable toxicity, or occurrence of any criterion for withdrawal from the trial or the IMP (see Section 5.5).

Subjects who have experienced SD, PR, or CR should continue treatment through the end of 12 months, although additional treatment is possible. If the Investigator believes that a subject may benefit from treatment beyond 12 months, it may be permissible after discussion with the Medical Monitor and the Sponsor Medical Responsible. In the case of PD, subjects should continue treatment through their next tumor assessment, if they meet the criteria described in Section 5.5.1. If there is further evidence of PD thereafter, trial treatment should be discontinued; however, continued treatment is possible in consultation with the Medical Monitor. For subjects who achieve SD, a CR or PR on MSB0011359C therapy and then subsequently develop disease progression after stopping therapy, but prior to the end of the trial, 1 re-initiation course of treatment at the same dose and schedule and treatment duration up to 12 months is allowed at the discretion of the Investigator and agreement of the trial Medical Responsible (see Section 5.1.6). The Investigator will need to confirm that the benefit of re-initiating treatment outweighs any risk involved, such as that which led to initial treatment discontinuation. Moreover, for subjects in which BOR was SD, the Investigator should confirm no other reasonable treatment options are available.

For subjects in the melanoma, SCCHN, and TNBC cohorts only, symptom severity will be assessed using 2 patient-reported outcomes questionnaires:

- Patient Global Impression of Severity (PGIS)
- Select items from the EORTC QLQ-C30

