5.1.3.2 Dose Escalation

The dose escalation will use a standard 3 + 3 scheme with the following planned doses (once every 2 weeks):

- 1 mg/kg
- 3 mg/kg
- 10 mg/kg
- 20 mg/kg
- 30 mg/kg
- 2400 mg flat dose

The DLT period is defined as 21 days after the start of therapy. The first subject of each cohort will be observed for at least 5 days before the second subject can be treated. Thereafter, within each cohort 48 hours must pass before a new subject can initiate dosing. Once the 3 or 6 subjects have passed the 21-day DLT evaluation period the SMC will review the safety and available PK data to decide upon further dose escalation. Pharmacokinetic data from the previous cohort will be required for SMC review (for example, when the SMC is reviewing safety data from the 10 mg/kg cohort, available PK data from the 3 mg/kg cohort); however, PK data from the cohort under review will not be required.

The criteria for moving from 1 dose level to another do not allow escalation to the next cohort in cases where ≥ 2 of 3 or 6 subjects in a cohort experience a DLT. If 1 DLT in 3 subjects is observed, this cohort will be automatically expanded to 6 subjects with SMC meeting after the 6th subject completes the DLT evaluation period. Likewise, if at the highest dose level (30 mg/kg) no DLTs occurred in the first 3 subjects, the cohort may be expanded to 6 subjects with SMC meeting after the 6th subject completes the DLT evaluation period.

The MTD is defined as the highest dose where fewer than 2 of 6 subjects experience a DLT. Thus, the MTD cohort should accrue a total of 6 subjects. If 1 of 6 subjects has experienced a DLT at a dose below 10 mg/kg, dose escalation will be modified (Table 4).

The DLT criteria will not apply to any of the expansion cohorts.

Table 4 Modification of Dose Escalation Based on DLT Observations

Dose Escalation Schedule Scenarios	Dose of MSB0011359C (mg/kg)	
	No DLT at Dose Level	DLT at Level 1 (1 mg/kg) or DLT at Level 2 (3 mg/kg)
Level 1	1 mg/kg	1
Level 2	3 mg/kg	3
Level 3	10 mg/kg	7 ^a
Level 4	20 mg/kg	10
Level 5	30 mg/kg	20
Level 6	2400 mg	No modification

DLT = dose-limiting toxicity.

a If 1 of 6 subjects has a DLT at dose level 1 or 2.

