5.1.8 Analysis Cutoff Dates

After the end of the dose-escalation part of the trial, a full analysis for safety and PK / CCI data will be performed. The data cutoff date will be 6 weeks after the last subject of the escalation part has received his /her first administration of MSB0011359C. At the time of this amendment when adding the 2400 mg flat-dose cohort, the full analysis for the dose-escalation part of the trial had been completed. For the 2400 mg flat-dose cohort, an analysis will be performed at least 6 weeks after last subject first dose.

For the HCC ascending-dose cohort, an interim analysis will be conducted 12 weeks after the 30th subject in the 1200 mg ascending-dose portion received the first dose.

For the NSCLC anti-PD-1 / anti-PD-L1 failure cohort, an interim analysis will be conducted 12 weeks after the 40th subject in the cohort started treatment.

For the melanoma anti-PD-1 / anti-PD-L1 failure cohort, NSCLC second-line, pancreatic adenocarcinoma, CRC, TNBC, ovarian cancer, esophageal adenocarcinoma, SCCHN, glioblastoma, and cervical cancer cohorts, an interim analysis for that cohort will be conducted 12 weeks after the 30th subject in the cohort started treatment.

The primary data cutoff for the analysis of each expansion cohort separately will be 24 weeks after the last subject in that cohort started treatment (60th subject for the HCC cohort).

Final data cutoff will be after subjects are either enrolled into a roll-over trial or withdrawn after completing at least the Safety Follow-up visit at 10 Weeks (± 2 weeks) after Last Treatment (see Table 1).

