6.2 Dosage and Administration

Subjects will receive IV infusion of MSB0011359C over 1 hour (-10 minutes / +20 minutes, that is, over 50 to 80 minutes) once every 2 weeks as detailed in the Schedules of Assessments (see Table 1 and Table 2). Subjects enrolled in the 30 mg/kg and the 2400 mg flat-dose cohorts who require a drug volume of 500 mL may have a total infusion time of up to 120 minutes in the absence of any history of infusion reaction. Modifications of the infusion rate due to infusion-related reactions are described in Section 6.5.4. In order to mitigate potential infusion-related reactions, premedication with an antihistamine and with paracetamol (acetaminophen) (for example, 25-50 mg diphenhydramine and 500-650 mg paracetamol [acetaminophen] IV or oral equivalent) approximately 30 to 60 minutes prior to each dose of MSB0011359C is mandatory for the first 2 infusions and is optional and at the discretion of the Investigator after the second infusion (premedication is optional for all infusions for subjects in the NSCLC biomarker cohort being treated at the US NCI). If Grade ≥ 2 infusion reactions are seen during the first two infusions premedication should not be stopped. Steroids as premedication are not permitted. Special precautions for monitoring of subjects and management of infusion-related reactions / hypersensitivity including modifications of the infusion rate and stopping of trial drug are described in Section 6.5.4 and subsections.

The starting dose of MSB0011359C in the dose-escalation portion is 1 mg/kg (dose-escalation according to 3 + 3 design up to 30 mg/kg is intended) and the treatment cycle will be 2 weeks (14 days). The first subject of each cohort will be observed for at least 5 days before the second subject can be treated. Subsequent subjects may receive first dosing at no less than 48-hour intervals between subjects. The dose of MSB0011359C in the expansion will be determined from the dose-escalation portion of the trial.

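### Section 6.5.4 and Table 5 drop the in-patient stay and dosing stagger once the expansion dose is declared, without excepting the uncleared 30 mg/kg and 2400 mg escalation cohorts

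*Protocol*

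**What the plan says.** **The relaxed rule (Protocol 6.5.4 and Table 5).** The opening sentence of 6.5.4 limits the 24-hour in-house stay for the first 2 doses to subjects enrolled before the MTD, or the expansion dose if no MTD is reached, is declared. A later paragraph lifts the wait from that point: "dose to be used in the expansion phase of the study has been declared there is no waiting period between dosing of subjects". The accompanying Table 5 has three columns:

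| | Before declaration, dose not cleared | Before declaration, dose cleared | After declaration |
|---|---|---|---|
| In-house stay | 24 hours | None | None |
| Wait after first subject | 5 days | 48 hours | None |

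The period before declaration is split by dose clearance; the period after is not. The only table footnote concerns the HCC ascending-dose cohort.

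**The strict rule (elsewhere in the Protocol).** Section 5.1.3.2, whose dose list includes 30 mg/kg and 2400 mg, states: "The first subject of each cohort will be observed for at least 5 days before the second subject can be treated", with 48 hours between later subjects. Section 6.2 repeats this: "Subsequent subjects may receive first dosing at no less than 48-hour intervals between subjects". Sections 6.4 and 7.1.2.1, the hospitalization row of Table 1 and its footnotes s and t require at least 24 hours in-patient for the first 2 escalation doses. Footnote s names the 30 mg/kg and 2400 mg cohorts. None of these rules ends when the expansion dose is declared.

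**Timing of the two cohorts.** Section 5.1.1.2: "The flat doses for extension part will be implemented after clearance of 20 mg/kg escalation cohort by the SMC". Section 5.1.1.1: after that same clearance, "additional cohorts at 30 mg/kg and 2400 mg flat dose will be initiated, in parallel to the ongoing expansion cohorts". The Synopsis and section 8.1.1 add that 2400 mg opens only once the safety of 30 mg/kg is established.

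**The concern.** Whether a subject is kept in hospital and staggered should depend on whether the dose has been cleared. Table 5 follows that logic before declaration and abandons it afterwards. The relaxation makes sense for expansion cohorts, which receive a dose already judged acceptable. It does not fit a new, higher 3 + 3 level that opens later. At 30 mg/kg the cohort's stated purpose is to "support safety considerations at higher exposures than the expansion-phase dose of 1200 mg once every 2-weeks" (Synopsis), so it explores exposures beyond the declared dose.

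The protocol therefore gives two different minimum precautions for the first subjects at a dose the SMC has not reviewed. At stake is the time available to see an acute or early toxicity in one subject before the next is dosed, and whether those subjects are in hospital for the first 24 hours. No efficacy endpoint, sample size or analysis is affected.

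**Working it through.** There is no statistical figure to reproduce. The check sets the provisions side by side and then works out the timing each implies.

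**Step 1: which Table 5 column applies?** The expansion flat doses follow clearance of 20 mg/kg (5.1.1.2). The 30 mg/kg and 2400 mg cohorts start alongside expansion cohorts already running (5.1.1.1). The 2400 mg cohort came later still: at that amendment, "when adding the 2400 mg flat-dose cohort, the full analysis for the dose-escalation part of the trial had been completed" (5.1.8). An expansion cohort cannot be running at a dose not yet chosen, so both cohorts fall in the after-declaration column. No MTD is needed for this, since declaring the expansion dose is enough.

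**Step 2: are these doses cleared when first given?** No. Each is a 3 + 3 level with SMC evaluation after the first 3 subjects (5.1.1.1). For 2400 mg the 30 mg/kg gate helps in part: 2400 / 30 = 80 kg, so subjects of 80 kg or more receive no more per kg than 30 mg/kg, and lighter subjects receive more.

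**Step 3: what does each reading require?**

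| | 5.1.3.2, 6.2, 6.4, 7.1.2.1, Table 1 | 6.5.4 and Table 5, literal |
|---|---|---|
| First to second subject | at least 5 days | 0 |
| Second to third subject | at least 48 hours | 0 |
| First to third subject | 5 + 2 = 7 days | 0 days |
| In-patient time per subject, doses 1 and 2 | at least 2 × 24 = 48 hours | 0 hours |

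There is an intermediate reading. Section 6.5.4 also asks staff to contact the first subject of each cohort "on or after Day 5 but before enrolling a subsequent subject". If that survives declaration and the 48-hour gap does not, the first-to-third minimum is 4 days (first dose counted as Day 1) to 5 days. The sentence sits in the paragraph about subjects enrolled before declaration, so its reach is unclear.

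**Step 4: how many subjects?** Two cohorts × 3 subjects before SMC evaluation = 6.

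**Step 5: does the cleared-dose column have the same problem?** Yes, for the stay. Table 5 shows *None* in-house once a dose is cleared. Table 1 footnote s and 7.1.2.1 require the stay for every escalation subject, whether or not the dose is cleared, and Table 1 also covers the backfill cohorts. The HCC 1200 mg ascending-dose cohort follows the expansion schedule (7.1.2.2), so *None* is consistent for it.

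**The case against.** The best defence is that the strict rule is stated many times, is specific to escalation and names these doses. Section 6.4 is even worded as an exception to the ordinary 2-hour observation. A site running these cohorts works from Table 1. *None* in Table 5 is only the absence of a minimum, so a site that admits and staggers its subjects breaches neither text. Other safeguards remain under any reading: the 2-hour post-infusion observation, vital signs to 6 hours after each of the first 2 infusions with the subject kept in clinic (Table 1 footnote i), and SMC evaluation after 3 subjects. The 2400 mg cohort also had the 30 mg/kg gate.

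All of this stands as to weight. The strict rules are probably what was intended, and practical risk is low. It does not make the text consistent. Table 5 is the table dedicated to wait periods, its title covers dose cohorts as well as expansion cohorts, and no clause says the other sections prevail. The protocol does write precedence where it wants it: section 5.1.7.2 says Table 7 may override it for immune-related reactions.

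Two stronger readings are tempting and not supported. A reader might infer that subjects at these doses were in fact dosed without a stagger or an in-patient stay; the documents give no dosing dates or admission records and nothing shows that a site followed Table 5. A reader might also count up to 12 subjects (2 × 6); under 5.1.1.1 the SMC evaluates after the first 3, so subjects 4 to 6 cannot be assumed to have been dosed before review.

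**Conclusion.** The inconsistency is real and sits in current text; no footnote or amendment entry resolves it. Read literally, 6.5.4 and Table 5 remove the stay and the stagger from two escalation cohorts for which the rest of the protocol requires them. It most directly concerns 6 subjects, with a first-to-third interval of 7 days against 0, and 48 hours in-patient per subject against none. These are bounds from reading the text, not observed effects.

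The conclusion assumes that declaration of the expansion dose had occurred by the time expansion cohorts were running, which the documents imply but do not date.

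Severity is minor. SAP section 6 lists both cohorts among dose levels already received, and last subject out for escalation was planned for Q3 2019 (Protocol 5.1.6), so the correction mainly puts the record straight and prevents reuse of the wording.

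**What to change.** Four text changes in section 6.5.4:

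1. Limit the after-declaration column of Table 5, and the sentence removing the waiting period, to expansion cohorts.
2. Amend the opening sentence so that the 24-hour stay for the first 2 doses applies to dose-escalation subjects whenever they are enrolled, including those at 30 mg/kg and 2400 mg.
3. State that the 5-day then 48-hour stagger applies to each 3 + 3 escalation cohort whenever it opens.
4. Align the in-house cell for cleared doses with Table 1, footnote s and 7.1.2.1 for escalation and backfill subjects, keeping *None* only for the HCC ascending-dose cohort.

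Changing the after-declaration column alone would not be enough: the opening sentence would still end the stay at declaration, and the cleared-dose cell would still contradict Table 1. After change 1, backfill subjects enrolled after declaration would have no wait cell, so the text should also say which wait applies to them.

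The cost is a few lines of protocol text, with no effect on sample size, endpoints or analyses.
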